## Statistical Analysis Plan

**Cohort creation and observation time.** The study cohort will include outpatients receiving maintenance hemodialysis at a study center at any time between April 3, 2017, and March 31, 2021. The patient’s cohort entry date is their index date. Patients will be analyzed according to their initial center’s random allocation on their index date (ie, all outcome events will be attributed to that center [the index center] according to the intention-to-treat principle); for new patients who initiate dialysis during the trial follow-up, the index center is the dialysis center where they entered the cohort. Patients will be followed for study outcomes until death or the trial

end date on March 31, 2021. Based on emigration rates in Ontario, we estimate that 0.5% of patients will permanently leave the province every year during follow-up and approximately 85% of patients’ observation time will be spent receiving maintenance hemodialysis at their index center (or at another center with the same random treatment allocation). The treatment allocation does not follow patients who transfer to another hemodialysis center during follow-up; rather patients follow the new center’s dialysate temperature protocol.

**Analysis of adherence to the allocated temperature protocol.** Prior to the analysis of the primary outcome, we will assess adherence to the allocated temperature protocol for each month during follow-up and overall for each arm of the trial. The adherence at the center level will be weighted by center size. We will also report the proportion of time patients spend on their index center’s treatment allocation.

**Analysis of the primary outcome.** Our analyses will account for the design and covariate-constrained randomization. In the primary intention-to-treat analyses, we will also assess the effect of the intervention on the rate of the composite outcome of cardiovascular-related death or hospitalization using the multivariable generalized-estimating-equations extension for the Cox proportional hazard model, with an exchangeable covariance matrix, to account for the clustering of individuals within hemodialysis centers. Patients will be censored at end of study follow-up or earlier if they die due to a non-cardiovascular-related cause. Patients who recover renal function, switch to a hemodialysis center with the alternative or no temperature allocation, receive a kidney transplant, or switch to home dialysis will be followed for outcomes according to their initial random allocation (see “Additional Exploratory Analyses” section).

**Analysis of secondary outcomes.** Between-group mean differences in the drop of mean systolic blood pressure is the key secondary outcome, because it examines the mechanism through which a lower dialysate temperature is expected to improve outcomes. This outcome will be analyzed at the center level using a repeated-measures random-effects linear mixed model. This model will provide an estimate (with 99% confidence intervals—see “Statistical Significance” section) of the absolute mean difference in the intradialytic drop in systolic blood pressure between the 2 groups.

For the analysis of the other secondary outcomes, the same approach described for the primary outcome will be used to analyze each component individually (eg, cardiovascular-related death, hospital admission with myocardial infarction) and the other secondary time-to-event composite outcomes (ie, all-cause mortality or cardiovascular-related hospitalization). Noncardiac death (except for outcomes that include all-cause mortality) will be treated as censoring events in these analyses. Model fit will be assessed to ensure

that all assumptions are met (eg, proportional hazards). If proportional hazard assumption is violated, we will explore using a time-stratified Cox model.

**Bayesian analysis of the primary outcome.** We will assess the robustness of the primary findings (based on the classical frequentist analytic approach) to various assumptions about the use of prior information from various sources. As a supplement, we will conduct and report a Bayesian analysis based on existing guidelines. Our aim is to determine the probability that the intervention (1) has any effect on the primary outcome and (2) reduces the hazard rate of the primary outcome by at least 5%, 10%, 15%, 20%, and 30% given the observed data. We considered a minimum 5% hazard rate reduction (ie, hazard ratio = 0.95) in the primary composite outcome as clinically relevant as it would translate to an estimated 150 lives saved or major cardiovascular-related hospitalizations prevented every year in Canada.

We will explore several prior distributions (Table 3) that can condition the posterior distribution and provide insight about the sensitivity of the primary results. We are using priors to reflect varying degrees of enthusiasm and skepticism for the benefit of personalized dialysate temperature before the start of the MyTEMP trial. See Supplemental Appendix 12 for more details.

**Analysis of other outcomes.** For the analysis of emergency department visits and all-cause hospitalizations (number of visits and length of stay), the incident rate ratio (visits/events per person-year) will be estimated using either Poisson regression or a negative binomial regression model (depending on the level of dispersion) accounting for within-center clustering. For the analysis of hospital encounters with major lower limb amputation and hospital encounters with major falls or fractures, the hazard ratio for time to first event will be estimated from a Cox model as described above for the primary outcome.

**Additional exploratory analyses.** We will perform several exploratory analyses to assess the robustness of the primary analysis. These analyses may include treating some events as competing rather than censoring events in follow-up and repeated events per patient (for the primary analysis)—see Supplemental Appendix 13 for more details.

In the literature, the credibility of subgroup effects is generally low, even when claims about the treatment effect made by the researchers are strong. We will visually examine the point estimate of the hazard ratio for the primary outcome with its accompanying 95% confidence intervals across subgroups for consistency of the effect. Two prespecified subgroups of interest, where a personalized dialysis temperature may have a larger treatment effect, are (1) patients with a baseline prior hospitalization with myocardial infarction, ischemic stroke, or congestive heart failure, and (2) incident patients, defined as new patients starting in-center hemodialysis during follow-up

(based on historical data, approximately 9000 patients will start hemodialysis at a study center during the 4-year trial period).

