## Statistical Power

Power calculations for the primary composite outcome of this trial are based on a comparison of hazard rates (accounting for clustering). To inform these calculations, we conducted a historical analysis of 15 233 patients who received maintenance hemodialysis at 84 Ontario centers in the 4-year period before the trial start date. Each center cared for a median of 122 patients (range, 17-736) and contributed a median follow-up of 258 person-years (range, 35-1524). During this period, the hazard rate for the composite outcome of cardiovascular-related death or hospitalization was 0.095 events per person-year (termed the baseline hazard). We used a coefficient of variation (the ratio of the between-cluster variance to the average baseline hazard rate) of 0.216, and a cluster harmonic mean of the total person-time follow-up of 163 person-years. Based on these data, our trial will have 80% power to detect a hazard rate reduction of at least 20% (corresponding to a hazard ratio of 0.80; 2-sided  $\alpha = 0.04$ ; 0.04 chosen to control the family-wise error rate, see “Statistical Significance” section). Supplemental Appendix 11a shows the statistical power achieved for various hazard rate reductions, coefficients of variation, and annual baseline hazard rates for the primary composite outcome. We also confirmed our power calculations through computer simulations that took into account other complex aspects of the study design, including variable cluster sizes, censoring, and different patient follow-up times (these analyses are detailed in Supplemental Appendix 11b and confirmed the trial will have 81% power for a 20% hazard rate reduction [or a hazard ratio of 0.80] in the primary composite outcome [2-sided  $\alpha = 0.04$ ]).

Assumptions for power calculations for the key mechanistic secondary outcome are presented in Supplemental Appendix 11c. We have 84% power to detect a 4 mm Hg between-group difference in the mean drop in systolic blood pressure with a 2-tailed  $\alpha = 0.01$  (0.01 was chosen to control the family-wise error rate, see “Statistical Significance” section), a standard deviation of 7.2, 6 repeated observations, constant conservative intraclass correlation coefficient (ICC) of 0.4, and an average drop across all sites and periods of 28 mm Hg.

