### Statistical Significance

In keeping with recommended practice, our aim is to avoid type I errors due to multiple comparisons. We will use the parallel gatekeeping procedure to control the overall family-wise error rate at 0.05. The first family of hypotheses includes both the primary and key secondary hypotheses (composite primary outcome and drop in intradialytic systolic blood pressure), with weights of 0.8 and 0.2, respectively. If the intervention improves at least 1 of the 2 outcomes in the first family of hypotheses, outcomes in a second family of hypotheses will be tested in the following order at a level of significance that maintains the overall error rate across all prior testing at .05: all-cause mortality or cardiovascular-related hospitalization, all-cause mortality, hospital admission with myocardial infarction, hospital admission with congestive heart failure, and hospital admission with ischemic stroke. Any reported confidence intervals that maintain the family-wise error rate at .05 will be adjusted for the tested level of significance.

The reporting of treatment effects on outcomes including secondary outcomes examined after the family-wise error rate exceeds 0.05, additional outcomes, prespecified and post hoc subgroup analyses, and exploratory analyses will be limited to point estimates with 95% confidence intervals (without *P* values), and we will indicate that these interval widths are not adjusted for multiple testing, so that inferences drawn from them may not be reproducible.

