## Statistical Principles

### Confidence Intervals and *P* Values: Level of Statistical Significance

We planned the trial using a parallel gatekeeping procedure to control the overall error rate at 0.05 (to control for multiple testing). The 2-sided significance level will be 0.04 for the primary hypothesis and 0.01 for the key secondary hypothesis.

The remaining secondary outcomes will be tested as follows: If the overall error rate for the primary hypothesis and key secondary hypothesis exceeds 0.05, the results of subsequent tests will be provided as point estimates with 95% confidence intervals (CIs; without *P* values), and we will indicate that the interval widths are not adjusted for multiple testing and that the inferences may not be reproducible.

If there is a statistically significant improvement in the primary outcome or the key secondary outcome, the remaining secondary outcomes will be tested in the following order at a level of significance that maintains the overall error rate across all prior testing at 0.05 (example below): (1) A composite of all-cause mortality or cardiovascular-related hospitalization, (2) all-cause mortality, (3) hospital admission with myocardial infarction, (4) hospital admission with congestive heart failure, (5) hospital admission with ischemic stroke, and (6) cardiovascular death.

For example, if the primary outcome is nonsignificant ( $P \geq .04$ ) and the key secondary outcome is nonsignificant ( $P \geq .01$ ), no further hypothesis testing will be performed. If the primary outcome is significant and the key secondary outcome is nonsignificant, then the remaining secondary outcomes will be tested at a significance level of 0.04 until a *P* value is  $\geq .04$ . If the primary outcome is nonsignificant and the key secondary outcome is significant, then the remaining secondary outcomes will be tested at a significance level of 0.01 until a *P* value is  $\geq .01$ . Once one of these tests exceeds an overall error rate across all prior testing at 0.05, as described above, the results of subsequent analyses will be limited to point estimates with 95% CIs (without *P* values), and we will indicate that the interval widths are not adjusted for multiple testing and that the inferences may not be reproducible.

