**Subgroup analyses.** In our protocol, we have prespecified two subgroup analyses for the MyTEMP trial. We will simply provide point estimates and corresponding 95% CIs for subgroups and will not perform significance testing. First, a subgroup analysis of patients with preexisting cardiovascular disease (ie, patients hospitalized with myocardial infarction, ischemic stroke, or congestive heart failure at least once before study entry). Second, a subgroup of new hemodialysis patients, that is, those starting in-center hemodialysis for the first time during the trial period. These analyses will follow the same approaches as described above. We hypothesize that the intervention may confer a larger absolute benefit to these 2 subgroups of patients. To examine the presence of additive interaction, we will calculate the hazard ratios (and 95% CI) between the intervention and control groups in patients with and without preexisting cardiovascular disease, and in new hemodialysis patients versus those who were already receiving dialysis when the trial started on April 3, 2017.

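### Neither the protocol nor the SAP estimates the between-subgroup difference: consistency rests on separate hazard ratios, and the SAP's additive-interaction aim has no matching estimate

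*Combined protocol and SAP*

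**What the plan says.** The final protocol (Statistical Analysis Plan, Additional exploratory analyses) first warns that subgroup claims usually deserve little credence. It then says "We will visually examine the point estimate of the hazard ratio for the primary outcome with its accompanying 95% confidence intervals across subgroups", the purpose being to see whether the effect is consistent. It names two subgroups "where a personalized dialysis temperature may have a larger treatment effect": patients with a prior admission for myocardial infarction, ischemic stroke or heart failure, and patients new to in-center hemodialysis. Its Statistical Significance section adds that "prespecified and post hoc subgroup analyses, and exploratory analyses will be limited to point estimates with 95% confidence intervals", without P values and with a caveat that the intervals are not adjusted for multiple testing.

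The SAP (Additional Analyses, Subgroup analyses) keeps the two factors: "We will simply provide point estimates and corresponding 95% CIs for subgroups and will not perform significance testing". It moves the hypothesis to the absolute scale: "We hypothesize that the intervention may confer a larger absolute benefit to these 2 subgroups of patients". It also states an interaction aim: "To examine the presence of additive interaction, we will calculate the hazard ratios (and 95% CI) between the intervention and control groups". The strata compared are prior cardiovascular disease versus none, and new versus existing patients.

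Neither section specifies an arm-by-subgroup term, a ratio of hazard ratios, a between-stratum difference in absolute risk, or a criterion for calling the strata consistent. The SAP plans an absolute risk difference only for the trial as a whole, and only if the primary result is statistically significant.

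**The concern.** Both documents ask a question about a difference between strata. Separate intervals describe each stratum's effect, not the uncertainty of that difference. The reader must supply an informal rule, and the common rules err in opposite directions. Comparing which interval excludes 1 can turn noise into a subgroup finding. Waiting for intervals that do not overlap can miss a real difference.

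The SAP has a second gap. Stratum hazard ratios measure neither additive interaction nor absolute benefit. Suppose the hazard ratio is 0.80 in both strata and the control rate is *r* in one and 2*r* in the other (an illustrative assumption). The ratio of hazard ratios is then 1, but the rate reductions are 0.2*r* and 0.4*r*. The SAP's hypothesis would be true and its planned output would not show it.

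The stake is how two prespecified, directional subgroup statements are described in the trial report.

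**Working it through.** **Inputs from the documents.** Final protocol, Statistical Power: baseline rate 0.095 per person-year, coefficient of variation *k* = 0.216, harmonic mean 163 person-years per centre, two-sided alpha 0.04, hazard ratio 0.80. Appendix 11a: 42 centres per arm. Table 2, footnote b: about 31 314 person-years in total.

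**Assumptions, not in the documents.** The smaller subgroup holds 20% to 50% of person-time. The protocol gives about 9000 new patients out of about 15 500 (58%), but no person-time share. Event rates and *k* are the same in both strata; letting the smaller stratum's rate be up to twice the other's stays within the ranges below. The correlation *ρ* of centre effects between strata is 0, 0.5 or 1. The calculation uses a rate formula, not the planned subdistribution-hazard model.

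**Step 1: reproduce the stated power.** With λ0 = 0.095 and λ1 = 0.076, the variance of the rate difference is [(λ0+λ1)/163 + *k*²(λ0²+λ1²)]/(42−1) = (0.001049 + 0.000691)/41 = 0.0000424, so the SE is 0.00651. Then 0.019/0.00651 − 2.054 = 0.863, which gives power 80.6% against the stated 80%.

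**Step 2: one worked case (50/50 split, hazard ratio 0.80 in both strata).**
- Person-years per arm: 163 × 42 = 6846, or 3423 per stratum. Expected events: 325.2 control and 260.1 intervention.
- Within-centre variance of the log hazard ratio: 1/325.2 + 1/260.1 = 0.00692. Between-centre part: 2*k*²/42 = 0.00222. The SE per stratum is √0.00914 = 0.0956.
- Chance that a stratum's 95% CI excludes 1: Φ(0.2231/0.0956 − 1.96) = 0.646.
- Chance that exactly one of the two does: with unshared centre effects, 2 × 0.646 × 0.354 = 46%. With fully shared effects, the bivariate normal gives 39%.
- With 31 314 person-years (15 657 per arm) the stratum SE is 0.0724. The corresponding figures are 23% and 18%.

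**Step 3: full range, equal true effects.**

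| Informal reading | Hazard ratio | 163 person-years per centre | 31 314 in total |
|---|---|---|---|
| One CI excludes 1, the other does not | 0.80 | 39–58% | 18–40% |
| Same | 0.90 | 28–32% | 31–43% |
| Same | 1.00 | about 9% | about 9% |
| One estimate lies outside the other's CI | 0.80 to 1.00 | 11–33% | 6–29% |
| CIs do not overlap | 0.80 to 1.00 | under 1% | under 1% |

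A 95% CI for the contrast itself would exclude equality in 5% of such trials by construction.

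**Step 4: precision of the contrast.** Treating the two intervals as independent, the worked case on 163 person-years gives an SE for the log ratio of √(2 × 0.00914) = 0.135. If centre effects are fully shared, the between-centre part cancels and the SE is √(2 × 0.00692) = 0.118, which is 13% smaller. Across the assumed shares on that input, the reduction is about 9–14% if fully shared, about 4–7% if half shared, and nil if unshared. On 31 314 person-years the first two ranges are about 17–26% and 8–12%.

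**Step 5: what the contrast could detect.** At a 50/50 split and 80% power (5% two-sided), the detectable ratio of hazard ratios is exp(2.80 × SE). This runs from 1.46 (unshared) to 1.39 (fully shared) on 163 person-years, and from 1.33 to 1.24 on 31 314.

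**The case against.** The plan is cautious. It labels these analyses exploratory, withholds P values, warns that the inferences may not be reproducible, and commits to no subgroup claim. Visual inspection is protocol wording; the SAP's subgroup section does not mention it. The protocol gives no criterion for consistency, so any error rate belongs to a rule that the reader supplies. A ratio of hazard ratios would not answer the SAP's absolute-scale question. Judging it by whether its CI includes 1 is close to a test, and the interval would be wide.

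Most of this stands, and it limits the point. A reader might infer that subgroups with the same true effect will often look discordant. The documents do not support that as a general statement: it holds if one compares which interval excludes 1 and the treatment works, and it fails for a non-overlap reading. A reader might also infer that precision from shared centres is simply lost. That depends on a between-stratum correlation that no document gives, and the SAP's planned adjustment for each centre's historical event rate would reduce the gain.

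What the objection does not remove is the missing estimate. Low credibility of subgroup claims is a reason to show the contrast's uncertainty, and a wide interval shows it honestly. The reporting limits in both documents allow an estimate with a CI and no P value.

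**Conclusion.** The point holds as a reporting and estimand gap of moderate weight. The protocol judges consistency from separate intervals. The SAP states an additive aim and produces only stratum hazard ratios. Neither estimates the between-stratum difference. With equal true effects, apparent discordance ranges from under about 1% to 58% according to the reading rule, the true effect, the subgroup share, the sharing of centre effects and the person-time figure. That spread is what having no known error rate means here. Any gain in precision from a joint model is modest on the protocol's own harmonic-mean input.

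The sizes rest on the assumed shares of 20% to 50%, a common coefficient of variation and the rate approximation. Nothing here touches the primary result or the family-wise error rate, and a reader should not infer that it does.

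**What to change.** - **Both documents.** For each of the two prespecified factors, fit one model with an arm-by-subgroup term and centre-clustered robust variance. Report the ratio of hazard ratios with its 95% CI, without a P value, beside the stratum hazard ratios. In the protocol's exploratory section, make this ratio and its CI the basis for describing consistency.
- **SAP subgroup section.** Also report the between-stratum difference in the absolute risk difference, from the cumulative incidence functions at a stated time that both strata reach. Give a 95% CI that accounts for clustering by centre. This is the scale of the additive-interaction and absolute-benefit aim, and it should not depend on the primary result being significant.
- **Keep** the exploratory label, the absence of P values and the multiplicity caveat.

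The cost is SAP wording, one added term per factor and a clustered interval for the risk contrast. No new data are needed. The contrasts will have wide intervals, which the report should say.

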### Economic Analysis

We are designing a cost-effectiveness analysis that will model the costs and health outcomes for implementing a personalized dialysate temperature compared with a usual dialysate temperature. The primary outcome is the incremental cost-effectiveness ratio (ICER), where the costs will be considered from the perspective of a universal health care system and health outcome will be life-years.

We will use a multilevel model to allow for the correlation between costs and outcomes while accounting for clustering. The results will produce an estimate of the incremental cost per month alive with an accompanying 95% confidence intervals. We will supplement our base case analysis with a probabilistic sensitivity analysis to quantify the level of confidence in relation to uncertainty in the model inputs (ie, relative treatment effects, transition probabilities, costs, and outcomes). Details of this substudy are not included in this protocol.

